### **C13. Data Analysis Plan: C13a. Quantitative Data Analysis Plan**

**Data screening.** Via frequency distributions and scatterplots, variables will be examined for unusual distributions, out-of-range, and extreme values. We will confirm randomization using chi-square tests, t-tests, and the Kruskal-Wallis nonparametric test. We will test assumptions and underlying statistical models during model fitting. For generalized linear models and multilevel models, we will examine the homogeneity of error, normality of residuals, linearity of relationships between independent and dependent variables, and outliers. For multilevel models, we will assess multivariate normality of random effects.

**Missing data.** All analyses will adhere to the intention-to-treat approach, which includes all participants assigned to their condition regardless of study completion (Wells, 1999). Multiple imputation (MI), an optimal technique for missing data (Graham, 2009), will include all participants and available data. For all MI analyses, 20 data sets containing plausible values for missing data will be constructed using the Amelia II package for R, which incorporates both cross-sectional and longitudinal information in data imputation (Honaker, King, Blackwell, 2012). Each data set will be analyzed separately and model parameters combined for inferential tests (Rubin, 1987). The missing at random assumption will be assessed using a sensitivity analysis in which a series of pattern-mixture models that adjust parameter estimates for missing data patterns (Hedeker & Gibbons, 1997), will be compared with basic models to identify any potentially non-ignorable missing data patterns.

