implemented using the R lmerTest package with a random intercept for clinic. The b path was assessed using generalized linear mixed models with a logit link function for a binary distribution using the lme4 package. **Aim 3 Hypotheses:** Adapted MBC protocols (i.e., tailored condition) will outperform routine weekly administration of PHQ-9s (i.e., standardized condition) with respect to clinically significant change in depression severity from intake to week 12. Depression severity was analyzed using linear mixed models with Satterthwaite degrees of freedom implemented using the R lmerTest package. Multiple imputation was used to estimate missing values across 20 datasets in which 22.8% of patients did not complete the 12-week interview. We first assessed whether there was a change in PHQ-9 between intake and week 12 in a mixed model containing patient status as a covariate and random intercepts for patient and clinic. Next, implementation group was added to the model. In addition, number of sessions, number of sessions that the PHQ-9 was recorded, and number of sessions that the PHQ-9 was discussed were added to the model. We also examined the interactions between new patient status and the focal variables. **Power calculations.** A power analysis for the multilevel models for Aim 1 was assessed with Monte Carlo studies in which power is the proportion of significant effects (2-tailed  $\alpha$ ,  $p < .05$ ) for parameters of interest observed over repeated analyses of simulated data (Muthén & Muthén, 2002; Thoemmes, Reiser, & MacKinnon, 2010) using MPlus (version 7). For each model, 10,000 data sets were simulated and analyzed. Data in the Monte Carlo studies were simulated with the goal of identifying the smallest detectable effect size with power  $> 80$ . Dropout was simulated to reflect an increase of 5% missing data per wave. Repeated measurements were nested within participants (ICC = .50) and participants were nested in sites (ICC = .05). Average effect sizes for Aim 1 analyses were computed using an approximation of Cohen's  $d$  for growth models (Feingold, 2009). Using this metric, we are sufficiently powered to detect effect sizes as small as  $d = .46$  for the clinician models ( $N = 150$ ) and effect sizes as small as  $d = .30$  for the client models ( $N = 500$ ). For Aim 2, we conducted power analyses for the hypothesized mediation effects with the same assumptions described above but with the use of effective samples size estimates (an ICC corrected sample size) based on a design effect adjustment (Bickel, 2007) in order to use standard effect size metrics. The  $\kappa^2$  effect size for mediation (.01, .09, and .25 represent small, medium, and large  $\kappa^2$  respectively) was computed (Preacher & Kelly, 2011). We are sufficiently powered to detect effect sizes as small as  $\kappa^2 = .16$  for the clinician models and effect sizes as small as  $\kappa^2 = .10$  for the client models. For Aim 3 analyses, we are sufficiently powered to detect effect sizes as small as  $r = .27$  for clinicians and as small as  $r = .21$  for clients. The planned sample sizes are consistently sufficient for detecting medium effect sizes for clinician outcomes and small effect sizes for client outcomes, with the power to treat site as a random effect based 6 sites per condition (Atkins & Baldwin, 2013).

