Welcome Packet, which will, contain the informed consent, authorization for the release of health information for research, and a stamped and return-addressed envelope will be sent to the client's address. The client will a \$5 gift card as compensation for PHQ-9 completion in the initial phone screen. If the client signs and returns the release of health information either via the pre-paid envelope or in person at their next session (additional information on the informed consent process can be found below in Section XII: Informed Consent Process), s/he is enrolled in the study. At this point the client will receive an additional \$5 compensation. If the client consents to research participation and the authorization for the release of health information for research, their verbal PHQ-9 and demographics data from the initial phone screen will be utilized as a baseline measure and be transported to IU for storage, given that the consent includes that the PHQ-9 completed for the eligibility screener and demographics questions can be used for the purposes of research. The 5-Axis diagnosis and employment, status, program activity involvement (i.e., type, start date, end date, care coordinator involved, face-to-face contact, location, reasons for discharge), date of first and last service, date of intake session, admission status (active/inactive), body mass index (BMI), age at BMI, demographics, medication use (i.e. prescription type, dosage, units, number of pills), and blood pressure (Appendix C.3) will also be retrieved from the clinician's intake report and health records to obtain information about comorbidities and functioning for all enrolled clients. This information will be retrieved by a trained Centerstone Research employee who will de-identify the information and then provide it to the research team.

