## **Phase 2 (Months 8-38)**

*Client's Treatment (weeks 0-11).* Clients in the standardized condition will be asked to complete the hard copy PHQ-9 forms in the waiting room prior to every session with their enrolled study clinician, while clients in the tailored condition will complete the PHQ-9 according to the measurement-based care guidelines defined by the implementation team at each site. In all cases, clients will fill out the hard copy PHQ-9 prior to a session located in waiting room kiosks and completing the survey should only take about five to ten minutes. The client will then hand the completed PHQ-9 to his or her clinicians who will then enter it into the electronic health record so that the clinicians can review the PHQ-9 scores with the clients during the session. The CRI RA will pull the PHQ-9 data for all enrolled clients across the course of their treatment and provide it to the research team using the 9-digit anonymous identification number. In addition to the PHQ-9, clients will be asked to respond to a telephone or text message-based survey after each psychotherapy session to inquire as to whether their clinician discussed PHQ-9 scores in the session immediately preceding (Yes/No/NA) (Appendix C.4). Client can earn \$2 for every survey they complete for up to \$20. So clients may be able to earn an additional \$20 for completing these surveys after each session and the amount attained will be mailed with the \$10 incentive for completing the week 12 PHQ-9 (described below).

*Client's Treatment (week 12).* Clients will be reassessed for depression symptom severity via a phone interview (like the initial screen) at week 12 of their treatment, regardless of number of treatment sessions attended (Appendix C.2). A postcard reminder may be sent to clients before the phone interview as a reminder. The project coordinator and CRI RAs will track client time since entering treatment, beginning with the intake assessment. Clients will be mailed \$20 as an incentive for completing the week 12 assessment.

*Client's Treatment (week 13 and beyond).* Upon completion of the telephone assessment at week 12, PHQ-9 data collection for all enrolled clients will continue to occur according to the site guidelines for the duration of the study funding-period.

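### With only intake and week 12 in the depression model, the planned pattern-mixture check cannot tell random from non-random loss of week-12 PHQ-9 scores; a delta-adjusted analysis should be added

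*Combined protocol and SAP*

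**What the plan says.** C13a (Missing data) plans multiple imputation that "will include all participants and available data", with 20 data sets from software that "incorporates both cross-sectional and longitudinal information in data imputation". The missing-at-random assumption is then to be examined with "a series of pattern-mixture models that adjust parameter estimates for missing data patterns". These "will be compared with basic models to identify any potentially non-ignorable missing data patterns". The section names no dropout patterns, identifying restriction, shift range or decision rule. It does not say which outcomes or occasions the check covers.

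Depression severity is modelled in C13a under Aim 3: "We first assessed whether there was a change in PHQ-9 between intake and week 12 in a mixed model". Implementation group is added next. The same paragraph reports that "22.8% of patients did not complete the 12-week interview", without counts or a split by arm.

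On the data themselves, Section VII (Clients, Phase 1) says of consenting clients that "their verbal PHQ-9 and demographics data from the initial phone screen will be utilized as a baseline measure". For session scores, Section VII (Clients, Phase 2) says: "The CRI RA will pull the PHQ-9 data for all enrolled clients across the course of their treatment". Table 5 likewise lists the PHQ-9 at all sessions.

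**The concern.** A pattern-mixture model estimates the outcome separately by missing-data pattern. For a change over time, that requires the incomplete pattern to show some change. In a two-occasion model with a complete intake score there are two patterns: both scores, or intake only. The second pattern shows no change at all, so the comparison that the check needs is unavailable unless an assumption is brought in from outside, and the plan states none.

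Client depression severity is half of the co-primary Aim 1 (H1b), and the Aim 3 model is the only analysis of it described in C13a. A check that cannot respond to non-random loss gives a reader no information about the main threat to that comparison, although it is listed as the safeguard.

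**Working it through.** **Inputs.**
- Occasions in the model: intake and week 12 (C13a, Aim 3).
- Intake score: the phone-screen PHQ-9, which eligibility requires, so it is taken as complete.
- Missing at week 12: 22.8% (C13a, Aim 3). This cannot be reproduced because no counts are given. The planning allowance can be: 500 / (1 - 0.20) = 625, the recruitment figure in C12b. A 22.8% loss from 625 would leave 625 x 0.772 = 482.5, about 482.
- Clinically significant change: 5 PHQ-9 points (C4).

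**Step 1: observed rows.** Let D = 1 for a client without week 12, G = arm, and t = occasion. The pattern-mixture mean has eight terms: intercept, t, G, G x t, D, D x t, D x G and D x G x t. Clients with D = 1 have only the intake row (t = 0), so D x t and D x G x t are zero in every row. For 625 clients with 22.8% intake-only, the design has rank 6 of 8 (3 of 4 without arm). The estimable D terms describe intake and say nothing about week 12.

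**Step 2: imputed data.** Imputation under missing-at-random draws week 12 from the relation seen in completers. The true week-12 scores of non-completers never enter, so the result cannot depend on them. A simulation shows this: 625 clients, 600 replicates, 20 imputations, pooling by Rubin's rules. Assumed values are intake mean 15 and SD 4.5, week-12 mean 11, slope on intake 0.5 and residual SD 5. Missing scores were shifted by delta = 0, 1, 3 or 5. The test is D x t, the difference in change between patterns.

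| Log-odds of missing per SD of intake | Rejection, every delta | Pattern difference in change, every delta | Imputed mean change, every delta | True mean change, delta 0 / 1 / 3 / 5 |
|---|---|---|---|---|
| 0 | 0% | -0.01 | -4.00 | -4.00 / -3.77 / -3.32 / -2.86 |
| 0.3 | 0.2% | -0.68 | -4.02 | -4.01 / -3.78 / -3.31 / -2.85 |
| 0.6 | 31% | -1.29 | -4.02 | -4.01 / -3.77 / -3.28 / -2.80 |

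Rejection depends on how strongly missingness follows intake and not at all on delta. The 31% arises because change has slope 0.5 - 1 = -0.5 on intake. Clients with higher intake scores are missing more often, and their imputed change is larger. That is so at delta = 0 too, when missing-at-random holds.

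**Step 3: size.** With missing shares m and shifts delta by arm, the arm contrast moves by m_T x delta_T - m_S x delta_S (T tailored, S standardized).
- Shift in one arm only, 22.8% missing there: 0.228 x 1 = 0.23; 0.228 x 3 = 0.68; 0.228 x 5 = 1.14 points.
- Equal shift and equal missingness: 0.
- Equal shift with an assumed split of 17.8% and 27.8%: 0.10 x delta = 0.10, 0.30 and 0.50 points.

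For scale, C13a gives d = .30 as the smallest detectable client effect. If the PHQ-9 SD is between 4.5 and 6 (an assumption), that is 1.35 to 1.8 points, so 1.14 would be 84% to 63% of it.

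**Step 4: session scores.** If non-completers have a session score between the two occasions, the same eight-term design reaches rank 8 of 8. It was still 8 when about 5% of non-completers had one, although precision would be poor, and 7 when about 1% did.

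**The case against.** The strongest reply is that the trial holds more data than the two-occasion model uses. Session PHQ-9s are collected throughout treatment, and the imputation is to use all available data. The 22.8% missed a telephone interview, which is not the same as leaving treatment, so some may have scores near week 12. This stands: a growth-type pattern-mixture model would be estimable for non-completers with session scores. A reader might infer that the check can never be estimated for depression; the documents do not support that.

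Three limits remain:
- The documents do not say that session scores enter the imputation or the check, or how many non-completers have them.
- Whether a PHQ-9 was recorded is itself a fidelity outcome compared between arms, and its scheduled frequency can differ by arm. C12b adds the week-12 call for that reason. In the pilot (C9), use was 13.4% and 38.6% of possible administrations.
- Projecting an incomplete series to week 12 still needs an assumption that those data cannot test.

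A second reply is that the two-occasion model sits under Aim 3, which is exploratory, while the Aim 1 client power work refers to growth models with dropout per wave. But the Aim 1 text in C13a covers fidelity only and gives no separate depression model for H1b. The general Missing data paragraph has to serve that outcome.

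A reader might also infer that the check would always pass, so that the missing scores would be declared harmless. The plan sets no decision rule and makes no such statement, and Step 2 shows that the check can raise a flag. The flag simply carries no information about non-random loss.

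**Conclusion.** The point holds for the two-occasion depression model. There, the planned check cannot distinguish missing-at-random from non-random loss: the terms it needs are unidentified on the observed rows, and on imputed data its result does not depend on the true shift. These two results follow from the structure of the data. Only the rejection percentages rest on the simulation's assumed means, SDs and slope.

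The possible effect on the arm contrast is 0.23 to 1.14 PHQ-9 points for a one-arm shift of 1 to 5 points, if 22.8% of that arm is missing. The 1.14 is a scenario and should not be read as an expected error: the documents give neither the shift nor the split by arm, and the effect is nil when both are equal across arms. Nor is this a case against pattern-mixture models elsewhere in the plan. Outcomes with three or more occasions, such as the clinician surveys and the multi-month fidelity data, do not have this problem of structure.

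**What to change.** In C13a (Missing data), make these changes:
- For week-12 PHQ-9, add delta-adjusted multiple imputation as the sensitivity analysis for non-random loss. Add 0, 1, 2, 3, 4 and 5 points to the imputed week-12 values, in both arms together and in each arm alone. Report the shift at which the arm conclusion changes.
- Report the number and percentage missing week 12 by arm.
- State whether session PHQ-9 scores enter the imputation and, if a pattern-mixture model is still fitted to depression, whether they enter that too and how it projects to week 12.
- Leave the pattern-mixture check in place for outcomes with three or more occasions, including the clinician surveys and the multi-month fidelity outcomes.

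The cost is SAP wording and a short rerun. Five non-zero shifts in three settings plus the zero case make 5 x 3 + 1 = 16 analyses, or 16 x 20 = 320 model fits on the existing imputed data sets. No new data are needed.

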Phase 1: Pre-Implementation (Months 0-8). The PHQ-9 and fidelity measures will be embedded in the EHR and the PHQ-9 linked to tablet computers for client completion to promote feasibility. Phase 2: Randomized Implementation Trial: Dynamic Waitlist Control (Months 8-38; Sites:  $N=12$ ; Clinicians:  $N=150$ ; Clients:  $N=500$ ; mixed within- & between-subjects design). MBC implementation will occur across 4 cohorts (2-4 sites) at early and later stages (each with 5-months active implementation, 10-months sustainment) to reduce confounds (timing) and increase feasibility (phased training). Both conditions will enact the 5 strategies within the active implementation period. We will use rapid ethnography (month 1) to synthesize the needs assessment data and develop the tailored content. Phase 3: Characterization of MBC Fidelity (Months 38-48). MBC fidelity will be coded, clinician and client fidelity reports will be triangulated, and sustainment will be evaluated.

**Specific Aims.** The hybrid design yields one co-primary aim (outcomes at the clinician- and client-levels) and two secondary exploratory aims in the context of a pragmatic trial (Thorpe et al., 2009).

**Aim 1:** To compare the effect of standardized versus tailored MBC implementation on clinician-level (**1a**) and client-level (**1b**) outcomes. We hypothesize that tailored implementation will outperform standardized in terms of (**H1a**) MBC fidelity, and (**H1b**) reducing client depression severity.

**Aim 2:** To identify contextual mediators of MBC fidelity. We hypothesize (**H2**) that contextual mediators (structure, norms, etc.) will be leveraged in the tailored condition, but serve as barriers in the standardized condition.

**Aim 3:** To explore the impact of MBC fidelity on client outcomes (Chambers et al. 2013). We hypothesize (**H3**) that adapted MBC protocols (tailored condition) will outperform weekly administration of PHQ-9s (standardized condition) with respect to clinically significant change in depression severity from intake to week 12.

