## **C. APPROACH**

**Overview.** Given the underwhelming use of MBC in community mental health settings coupled with the demand for performance outcome assessment (Affordable Care Act), this randomized implementation trial aims to compare the effectiveness of a standardized versus tailored approach to implementation of MBC with co-primary outcomes at the clinician (MBC fidelity) and client (depression severity) levels. We will randomize 12 sites of a large community mental health center (Centerstone) to early or later stage standardized or tailored implementation enrolling 150 clinicians and 500 depressed clients in a pragmatic trial (Thorpe et al., 2009). The main clinician level outcome is MBC fidelity, defined as (a) client completion of the PHQ-9, (b) clinician review of scores in the electronic health record, and (c) discussion of scores in session. Phase 1 (months 0-8) will interface the most widely used and validated depressive symptom severity measure (Patient Health Questionnaire-9 item; PHQ-9; [name], 2001) with the electronic health record; this measure is the main client level outcome. Phase 2 (months 8-38) constitutes the active implementation (5 months) and sustainment (10 months) phase. In both conditions, clients will have the option to complete the PHQ-9 on tablets in the waiting room prior to session, which will feed scores to clinicians via the electronic health record. Sites randomized to the standardized condition will begin with a baseline mixed methods needs assessment (for the purposes of putative mediator data collection) and receive the guideline that MBC is to be used in each session with a depressed client. The standardized condition will include manualized training and triweekly group consultation with experts to promote MBC fidelity and optimize its clinical utility. An implementation team (including a site administrator, opinion leader, MBC champion, and research personnel) will convene prior to each triweekly group consultation to review progress and troubleshoot problems. Sites randomized to the tailored condition will also begin with a needs assessment to identify contextual factors that may serve as barriers to the implementation (guided by the *Framework for Dissemination*; [name] et al., 2008; see C7). Training and triweekly group consultation will be tailored to address these barriers (e.g., clinician attitudes toward MBC). The implementation team (same composition as in standardized) will define a site-specific guideline for MBC use (e.g., monthly) and convene prior to each triweekly group consultation to troubleshoot MBC fidelity barriers. At the start of the active implementation across both conditions, depressed clients of participating clinicians will be enrolled to compare the effect of standardized versus tailored MBC implementation on client outcomes. Phase 3 (months 38-48) will characterize MBC fidelity using electronic health record data capture. The evaluation approach is guided by the *Framework for Dissemination* ([name] et al., 2008) and includes a baseline needs assessment, implementation/process evaluation (5 months into implementation), and outcome/impact evaluation (15 months into implementation). This design will allow for a direct test of the assumption that voltage drop in treatment outcomes occurs in the context of adapting the intervention to fit the context (Chambers et al., 2014), while simultaneously exploring the effect of standardized and tailored approaches to MBC implementation.

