**Aim 1: Hypotheses:** Tailored implementation will outperform standardized in terms of (H1a) fidelity. MBC clinician fidelity was evaluated with two variables: (1) whether the PHQ-9 was recorded in the EHR, and (2) among encounters for which the PHQ-9 was recorded, whether it was discussed. Both outcomes were modeled using generalized linear mixed models with a logit link function for a binary distribution using the lme4 package. All models included random intercepts for clinicians and patients. Models for both outcomes were constructed in an identical sequence. Models comparisons in the model-building sequence described below were evaluated using the Bayesian Information Criterion (BIC); the model with the better BIC was selected for presentation. Several unconditional growth models (i.e., models with only parameters for time) were fit (i.e., linear, quadratic, log-transformed number of months). After establishing the unconditional growth model, additional fixed effects were added in the following sequence: (1) group main effect and (2) group x time interaction. Finally, new versus existing patient status was investigated as a main effect using a dummy variable for new patient status and as a patient status x group interaction.

**Aim 2: Hypotheses:** Contextual mediators will be leveraged in the tailored condition, but serve as barriers in the standardized condition. Mediation models were fit to evaluate which contextual factors (based on clinician-completed surveys, Table 5; and, clinician selection of drop-down menu reasons for MBC deviations captured in the electronic health record) mediate the impact of the implementation condition on both clinician- and client-level outcomes. The two critical effects underlying mediation were evaluated in separate models: treatment condition predicts the mediator (path *a*) and the mediator predicts the outcome (path *b*). Specifically, mediators were assessed at the conclusion of the implementation window and the mediators were used to predict PHQ9 completion in the sustainment window. The *a* path was assessed using linear mixed models with Satterthwaite degrees of freedom

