#### **C15. Justification & Feasibility.**

We selected an effectiveness-implementation hybrid to investigate one co-primary aim that focuses on (1) implementation outcomes at the clinician level and (2) effectiveness with respect to client outcomes. To test the Dynamic Sustainability Framework (Chambers et al., 2013), we will need to compare the clinical effectiveness of the adapted use of MBC (tailored) as compared to the empirically supported MBC approach (standardized). Simultaneously, because no studies have attempted to scale up MBC in community mental health, we need to evaluate the implementation (clinician-level: fidelity) outcomes. The effectiveness-implementation hybrid design type 2 was identified as the optimal and innovative design solution for this proposal.

Within the effectiveness-implementation hybrid design, we will randomize sites to condition using a dynamic waitlist controlled approach. Half of the sites will receive a standardized approach to implementation and the other half will receive a tailored approach. This design reduces the effect of management- or clinician-level readiness or client factors that might otherwise confound the training effects allowing for unbiased data (Brown, et al., 2006). This design also affords the opportunity to conduct blocking on smaller time units and statistically provides large gains in efficiency (range from 33 to 100% gains). Moreover, training efficiency is achieved as not all sites must be trained at once, therefore allowing the same trainer(s) to train all sites to reduce any possible effect at the level of trainer expertise (Herschell, Kolko, Baumann, & Davis, 2010).

We have already piloted many of the implementation strategies and the evaluation approach (*C8: Pilot Studies*). Moreover, Centerstone has successfully completed >150 studies since 2003; two of these studies were NIMH-sponsored (CATIE, Keefe et al., 2007; STAR\*D, Insel, 2006), whereas others involved wide-scale implementation of EBPs for SAMHSA-sponsored program evaluations. Co-I ([name]) has coordinated many of these multi-site clinical trials at Centerstone. This proposal’s design considerations and the established strong collaborative relationship of our investigative team, we have no concerns regarding this proposal’s feasibility.

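### Client depression severity is declared co-primary (H1b), but the analysis plan assigns it no test: the only between-arm depression model sits under exploratory Aim 3, with no change contrast or deciding fit named

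*Combined protocol and SAP*

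**What the plan says.** **Status of the outcomes.** Section A states: "The hybrid design yields one co-primary aim (outcomes at the clinician- and client-levels) and two secondary exploratory aims". Aim 1 carries two hypotheses, H1a on MBC fidelity and H1b on "reducing client depression severity". The C. Approach overview describes the trial "with co-primary outcomes at the clinician (MBC fidelity) and client (depression severity) levels", and C15 repeats the structure: "We selected an effectiveness-implementation hybrid to investigate one co-primary aim that focuses on (1) implementation outcomes at the clinician level", with client effectiveness as the second element.

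**Aim 1 analysis (C13a).** The hypothesis is given as "Tailored implementation will outperform standardized in terms of (H1a) fidelity". The outcomes follow: "MBC clinician fidelity was evaluated with two variables: (1) whether the PHQ-9 was recorded in the EHR", and, where it was recorded, whether it was discussed. H1b is not named here or anywhere else in C13a.

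**Aim 3 analysis (C13a).** The hypothesis begins "Adapted MBC protocols (i.e., tailored condition) will outperform routine weekly administration of PHQ-9s" and concerns clinically significant change from intake to week 12. The model described is a linear mixed model of depression severity with multiple imputation and random intercepts for patient and clinic. It first assesses change over time. Then: "Next, implementation group was added to the model". Numbers of sessions, of sessions with the PHQ-9 recorded and of sessions with it discussed are added after that.

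**Power (C13a).** For Aim 1, the smallest detectable effects are d = .46 for clinician models (N = 150) and d = .30 for client models (N = 500), at two-sided .05.

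**The concern.** A hybrid type 2 trial answers two questions of equal standing: whether tailoring improves clinicians' fidelity, and whether it improves clients' depression. Someone following C13a literally would test the first under Aim 1 and find no instruction for the second. The depression comparison they would reach next is headed by a different hypothesis, in an aim declared exploratory.

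Three things are left undecided. Which analysis tests H1b? Which of the successive Aim 3 fits supplies the arm comparison? And must both co-primary outcomes succeed, or is one enough? Each affects what the trial may conclude about clients. The second also affects what is estimated: session and PHQ-9 counts arise after randomization and may themselves be affected by condition, so a group coefficient adjusted for them is not the overall effect of assignment.

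**Working it through.** **1. The plan's own figure.** The detectable effect for Aim 1 client models is stated as d = .30 at 80% power with N = 500. The simple formula is d = (1.96 + 0.84) × √(4/N).

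- Independent clients: 2.80 × √(4/500) = .25.
- With 12 sites and the stated site ICC of .05: mean cluster size 500/12 = 41.7; design effect 1 + 40.7 × .05 = 3.03; effective N = 500/3.03 = 165; d = 2.80 × √(4/165) = .44.

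The stated .30 lies between these and is not reproduced. It comes from a Monte Carlo growth model whose number of waves and slope variance are not given, so it cannot be called wrong. What matters here is that an Aim 1 client model was powered while C13a describes none.

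**2. Hypotheses against analyses.**

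| Hypothesis | Status in Section A | Outcome named | Analysis in C13a |
|---|---|---|---|
| H1a | co-primary | fidelity | two logistic mixed models under Aim 1 |
| H1b | co-primary | depression severity | none assigned |
| H3 | secondary exploratory | clinically significant change | linear mixed model of continuous severity under Aim 3 |

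C4 gives a five-point PHQ-9 change as clinically significant, but the Aim 3 model analyses the continuous score. By outcome it fits H1b; by heading it belongs to H3. Neither hypothesis has a clearly assigned test. Aim 2 mentions client-level outcomes, but it is a mediation analysis and the outcome it specifies is PHQ-9 completion.

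**3. What the group term estimates.** The model is described as assessing change between intake and week 12, so both scores appear to be responses. Suppose the arms are equal at intake and differ by δ at week 12. With balanced data, a group main effect without a group-by-time term averages the two differences: (0 + δ)/2 = δ/2. It also absorbs any chance intake imbalance. It is not a test of differential change. The Aim 1 fidelity models do name a group-by-time step; the depression model does not.

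**4. Error rate under the two possible success rules.** The only alpha stated is two-sided .05, and no multiplicity or success rule is given.

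- Both co-primary outcomes must succeed: each is tested at .05, and the chance of a false joint claim does not exceed .05.
- Either may succeed, two independent tests: 1 − .95² = .0975. With an assumed correlation of .5 or .8 between the tests, simulation gives .091 or .078.
- Either may succeed, with the two fidelity variables and depression each counting: 1 − .95³ = .1426, again assuming independence.

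These rates follow from the missing success rule and would be the same wherever the depression model is placed.

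**5. Timing.** The Aim 1 to Aim 3 analysis text is in the past tense and reports that 22.8% of patients did not complete the week-12 interview. Week-12 completion was therefore known when that text was written.

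**The case against.** The strongest reply is that a suitable model exists. C13a gives a full severity model with imputation and clustering, and adds group before any session counts. Since its outcome is H1b's outcome, this can be read as a misplaced heading. That stands in part: it would be wrong to say depression is not analysed. What does not follow is that the model as described tests H1b. The plan neither links the two nor says which fit decides, and the group term it names does not test change.

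Three stronger readings are tempting and are not supported.

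- A reader might infer that the result could be claimed as confirmatory if positive and set aside as exploratory if null. No text states or implies such a rule. Three sections fix depression as co-primary, C4 calls the PHQ-9 the primary depression measure, and the power paragraph still counts client models under Aim 1. Setting a null result aside would contradict all of these.
- A reader might set the Aim 3 figure for clients (r = .21) against d = .30 as conflicting sensitivities for one contrast. The text does not say that r refers to the arm contrast. Aim 3 is about fidelity and client outcomes, and an r is also given for clinicians (.27), which suggests a measure of association. Two metrics for two questions are not a conflict.
- A reader might infer from the 22.8% that arm results had been seen. The documents do not say so.

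**Conclusion.** The point holds as a gap between the declared hypotheses and the analysis plan. H1b is co-primary in three sections and is powered under Aim 1, but no test is assigned to it. The only candidate model sits in an exploratory aim under a differently worded hypothesis, names a group term that does not test differential change, and leaves open whether the comparison is made before or after post-randomization counts enter.

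This rests on the text of C13a, which runs without a visible break from Aim 1 to the power paragraph; no figure needs to be disputed. The δ/2 result assumes that both scores are responses and that no group-by-time term was intended but left unwritten. The 9.75% and 14.3% figures assume independent tests, each at .05, with any one sufficient. They measure the cost of the absent success rule, not of the model's placement. The gap should be closed before the client-level result is presented as a co-primary finding.

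**What to change.** 1. **State H1b under Aim 1 with one primary contrast:** the between-arm difference in PHQ-9 change from intake to week 12, either as group by time or as week 12 adjusted for intake PHQ-9. Keep a random intercept for clinic and exclude session and fidelity counts. Moving the present model unchanged would not be enough.
2. **State the success rule.** If both co-primary outcomes must succeed, alpha stays at .05. If either may, adjust alpha and say whether the two fidelity variables count as one claim or two.
3. **Keep the session and fidelity-count models under Aim 3,** labelled exploratory. Either add the five-point-change analysis that H3 calls for or reword H3 to match continuous severity.
4. **Say which contrast the d = .30 figure refers to.**
5. **Disclose when the H1b contrast was specified** relative to access to week-12 data. A revision made now cannot by itself make the test prespecified.

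The cost is a short SAP revision, one respecified depression model and, if H3 is kept as worded, one added exploratory analysis. No new data are needed.
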